1.0 Lay Summary

1.1 Background

Patients having surgery are at high risk of complications, some of which can be life threatening. Identifying complications early makes them easier to treat and improves the outcome for the patient.

One of the ways patients are monitored for complications is by charting their vital signs: blood pressure, heart rate, breathing rate and temperature. The nurse looking after the patient will usually check these signs every four hours in the first few days after surgery. The vital signs are used to form a score, the National Early Warning Score (NEWS), which can alert if the patient becomes unwell. One of the problems with NEWS is that patients can deteriorate in the interval between monitoring, which can delay vital treatment.

The SensiumVitals[®] monitoring system measures heart rate, breathing rate and temperature continuously, and sends the information to a mobile phone carried by the nurse every two minutes. It is a wearable, wireless patch that is applied to the patient's chest after surgery, and alerts the nurse if the patient's vital signs become abnormal. This could help detect unwell patients earlier than traditional NEWS monitoring.

1.2 Aims

In order to test this theory, a study will be done comparing the SensiumVitals[®] system with NEWS monitoring. The main aim is to provide important information about whether the patch works and if it improves outcomes for patients admitted to surgical wards.

1.3 Participants

Patients will be asked to join the study if they are admitted to one of four surgical wards at St. James's University Hospital, Leeds. Many of these patients will be admitted prior to, or after, undergoing a surgical procedure. They will be given information about the study and will be allowed time to decide whether they would like to take part.

1.4 Methods

Patients will be randomly chosen to receive standard NEWS monitoring or both the SensiumVitals[®] patch and NEWS monitoring based on the bed they are admitted to on each ward. This decision is made by hospital bed managers, who are not involved in the study: it is a 'random' process and roughly half of the patients will be offered the new system. Patients will be followed during the course of their hospital stay, including any operation they have.

Information about the patients' hospital stay will be collected. This information will include the number of patients who develop sepsis (infection) and how quickly they are treated, whether they are moved to high-dependency wards and how long they stay in hospital. Information will also be collected regarding the number of patients who agree to take part in the study, those who do not and the reason for not taking part.

An important part of the study will be to assess how patients and nurses feel about the SensiumVitals[®] system. The patient's perspective of the study will be assessed in a number of ways: interviews, questionnaires and focus groups. Nurses' feedback will also be assessed in the form of interviews and a questionnaire.

1.5 Distribution of results

The results of this study will provide important information about the performance of the SensiumVitals[®] system, how patients and clinical staff feel about the system, and whether the new monitoring system improves outcomes for surgical patients. The results will be communicated to healthcare professionals, patients and the public through journal articles, press releases and presentations to charities, NHS Trusts and the media.

2.0 Background

2.1 Major surgery and complications

Surgery is important in the management of many medical conditions, accounting for 4.5 million hospital admissions, 11.2 million hospital bed-days, and a cost to the NHS of £1.5 billion per year(1). Surgery is high risk, with complication rates between 30% and 40% for major abdominal procedures. Complications add to the financial burden to the NHS and cause significant morbidity, and occasional mortality.

Patients who develop postoperative complications become progressively unwell, often over a short period of time. Early recognition of postoperative complications is crucial in reducing morbidity and preventing long term disability; for patients with septic shock there is an 8% increase in mortality for every hour of delay in antibiotic administration(2). Recognition of this important statistic has led to the national introduction of the Sepsis CQUIN (Commissioning for Quality and Innovation) which rewards Trusts for prompt recognition of sepsis and the initiation of intravenous antibiotics within one hour(3), ensuring that monitoring of patient deterioration will assume high priority.

The more unwell a patient becomes, the more likely they are to require higher level care, either on High Dependency Units (HDU; Level II) or Intensive Care (ICU; Level III). Escalation of care comes at significant cost to both the patient and the health service. Admission to Level II/III care is associated with poor patient outcomes. The average cost of a Level I bed is £433/day, as compared to £1033/day for a HDU bed, and £1351/day for an intensive care bed(4). Early detection and treatment of complications minimises the need for Level II/III care, improves patient outcomes, and produces significant cost savings.

2.2 Vital signs monitoring

2.2.1 National Early Warning Score

The current standard of care for monitoring patients in the postoperative period is to record their vital signs (blood pressure, pulse, temperature, respiratory rate) using the National Early Warning Score (NEWS). Derangements in individual vital signs are scored according to their magnitude, and the scores summated to reflect the patient's overall condition. A higher score indicates patient deterioration, the need for escalation of care, and is linked to an increased chance of death.

The NEWS is calculated intermittently, at intervals directed by the patient's condition. Typically, in the postoperative period NEWS will be calculated half hourly for the first few hours, and if the patient remains stable the frequency will decrease to 2-hourly and then 4hourly, until the patient is ready for discharge when the NEWS may be recorded only twice a day.

Although NEWS has proven benefit, it suffers from several drawbacks. A 2012 study evaluated early warning scores in patients 48 hours before an adverse event (5). 81% of

patients had a score indicative of deterioration, but recordings were 'mostly incomplete' with respiratory rate documented in 'only 30% to 66%'.

NEWS relies on manual observations, is time-consuming, and open to user interpretation. Vital signs are taken at predetermined intervals (typically 4-hourly), with patient deterioration possible between recordings. It has been suggested that the gap between observations is one of the primary failings of the NEWS system (6).

2.2.2 Continuous monitoring

A solution to the problem of inadequate monitoring frequency is continuous monitoring at the bedside. Continuous monitoring is used in Level II/III care, but is limited by "hard-wired" equipment, which tethers the patient to the bed space. This hinders patient mobility and potentially slows their recovery. One study tested ICU-style monitoring on a general ward and found that only 16% of patients remained connected in a 72-hour period (7).

2.2.3 SensiumVitals[®] monitoring system

SensiumVitals[®] is a new monitoring system that combines the benefits of a wearable, wireless patch with continuous monitoring of vital signs. The SensiumVitals[®] patch (see Figure 1) is CE marked and monitors heart rate, respiratory rate and temperature continuously. The data is transmitted wirelessly every two minutes to a central monitoring station or a mobile device carried by the nurse (see Figure 2). This alerts the healthcare worker when there is deviation from pre-set physiological norms, alerting staff to potential patient deterioration.

2.3 Rationale for the proposed study

It is hypothesised that the SensiumVitals[®] system, as an adjunct to standard NEWS monitoring, will allow earlier detection of postoperative complications. This should reduce morbidity, which in turn should result in a decreased need for high dependency/intensive care.

3. Study objectives

To evaluate the safety, efficacy and acceptability of a new, wearable, remote monitoring system (SensiumVitals[®]) for patients admitted to surgical wards, as compared to standard monitoring with the National Early Warning Score system alone.

4. Study design

This is a single-centre feasibility study. Patients will be selected on the basis they are admitted to one of four general surgery wards. We will include 500 patients, most of whom will undergo a surgical procedure during their hospital stay.

When patients are admitted to a general surgery ward, they are allocated a bed by a team of 'bed managers' based on clinical need and availability. Each of the participating general surgery wards is divided into 'bays' of four or six beds, and 'side rooms' which contain only one bed. Prior to the commencement of the study, each bay and side room on each of the participating wards will be randomly allocated to receive 'patched' patients, or NEWS-monitored controls. The randomisation of bays will be balanced for ward type, taking account of patient gender and surgical subspecialty.

Patients will be identified as potentially eligible to participate in the study and approached on admission to the surgical wards. At this point they will be given further information in the form of a patient information sheet regarding the study. Following a period of consideration, if they have decided to participate in the study they will receive the appropriate monitoring. Information will also be collected regarding the number of patients who agree to take part in the study, those who do not and the reason for not taking part.

For the duration of the study, when a patient is admitted to one of the participating wards, they will be allocated to one of the two study arms according to the bay or side room to which they are allocated by the bed managers. The bed managers are removed from ward-based care and the allocation of a patient to a particular bed is 'random' and avoids selection bias. Eligible patients in the 'patch' bays/side rooms will receive a patch and standard NEWS monitoring. Patients in the 'control' bays/side rooms will receive standard NEWS monitoring alone.

All usual nursing and medical care are permitted within both arms of the trial. This includes fluid balance monitoring, neurological observations, etc.

Roughly half of the patients (250) will be offered the new system. The devices are designed to be lightweight and unobtrusive, with a battery life of 5 days. Patients will be expected to wear the device for the duration of their hospital admission. The device will monitor the patient's heart rate, respiratory rate and temperature continuously, and send this information every two minutes to a mobile device carried by the patient's nurse. The information is also available on the ward computer monitors.

The patients will remain in their allocated study arm for the duration of their hospital stay. If a 'patched' patient is moved to a critical care bed during their admission, the SensiumVitals[®] monitoring will be temporarily suspended pending reinstatement depending on the ward bed to which they return. Every effort will be made to ensure that patients remain in the study arm to which they were originally allocated, and any non-compliance will be recorded. Analysis will be on an intention-to-treat basis.

Patients' participation in the trial will end when they are discharged from hospital. At this point, 'patched' patients will be invited to complete a questionnaire and /or undertake a structured interview regarding their experiences of wearing the patch. Patients will also be invited to attend one or more focus groups after discharge from hospital. Information regarding the admission will be collected once the patient has left hospital.

The staff nurses will be invited to complete a paper questionnaire in the form of a Modified System Usability Score. They will also be invited to undertake a structured interview regarding their experience of providing the new monitoring system.

4.1 Outcome measures

4.1.1 Primary outcome measure

• Time to treatment of sepsis, specifically time to administration of antibiotics after first evidence of sepsis.

According to a revised consensus conference definition in 2001, sepsis is defined by the presence of a likely source of infection and 2 or more criteria from a collection of clinical signs and laboratory investigations as follows (8)

• Temperature >38.3°C or <36.0°C

- Tachycardia >90 beats per minute
- Tachypnoea >20 breaths per minute
- o pCO² <4.3 kPa
- Hyperglycaemia (blood glucose >6.6 mmol/) in the absence of diabetes mellitus
- o Acutely altered mental status
- WBC count >12×10^9/L or <4×10^9/L

Of these, temperature, heart rate and respiratory rate will be the most pertinent to this study as it is these parameters that are monitored by both the NEWS score and the SensiumVitals® monitoring system. The primary outcome measure will be the time interval between the first evidence of sepsis on either or both monitoring tools and the administration of antibiotics to the patient.

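### Section 4.1.1 starts the primary-outcome clock on tools that show only vital signs, while its sepsis definition admits cases those tools cannot show

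*Protocol*

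**What the plan says.** Section 4.1.1 of the protocol does three things in turn.

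- It names the primary outcome: "Time to treatment of sepsis, specifically time to administration of antibiotics after first evidence of sepsis".
- It defines a case of sepsis by "the presence of a likely source of infection and 2 or more criteria from a collection of clinical signs and laboratory investigations". The list covers temperature, heart rate, respiratory rate, pCO2, blood glucose, mental status and white cell count.
- It singles out three items: "temperature, heart rate and respiratory rate will be the most pertinent to this study as it is these parameters that are monitored by both" NEWS and the patch. It then fixes the outcome as "the time interval between the first evidence of sepsis on either or both monitoring tools and the administration of antibiotics to the patient".

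Section 2.2.1 describes NEWS as the means to "record their vital signs (blood pressure, pulse, temperature, respiratory rate"). Sections 2.2.3 and 4 describe the patch as measuring heart rate, respiratory rate and temperature. Neither tool is described as showing a blood result, mental status or a source of infection.

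The protocol does not say whether one abnormal sign or two count as first evidence. It does not say when the infection source must be apparent, or how far back from the infection an abnormal sign may lie.

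**The concern.** Who counts as a case and when that case starts are set by different information. Caseness can be reached through criteria that neither tool shows, and it always needs an infection source, which neither tool shows. The start time is confined to the tools.

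Two consequences follow. First, some patients who meet the definition have no assigned start, or one that depends on an unstated choice. Second, nothing links the first abnormal vital sign to the infection being treated. Most patients will have surgery and the heart-rate threshold is only 90 beats per minute, so a derangement unrelated to infection could be taken as the start of an infective episode that came later.

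At stake is whether the primary outcome measures delay in treating sepsis. Two people abstracting the same notes could both follow Section 4.1.1 and record different intervals for the same patient.

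**Working it through.** The protocol gives no figure to reproduce here: Section 10.1 makes no sample size calculation and Section 5.1.3 plans no formal test. The check counts the ways of meeting the case definition and asks which have a start on the tools.

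**Inputs (Sections 4.1.1, 2.2.1, 2.2.3 and 4).** Seven criteria, 3 shown by both tools (temperature, heart rate, respiratory rate) and 4 not listed for either (pCO2, glucose, mental status, white cell count). Blood pressure, which NEWS records, is not one of the seven. Assumption: the tools show only what the protocol lists.

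**Pairs of criteria.** C(7,2) = 21.
- Two vital signs: C(3,2) = 3
- One vital sign and one other: 3 × 4 = 12
- No vital sign: C(4,2) = 6

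**All sets of two or more**, since the definition is not limited to pairs. 2^7 − 1 − 7 = 120.
- At least two vital signs: (3 + 1) × 2^4 = 64
- Exactly one: 3 × (2^4 − 1) = 45
- None: 2^4 − 1 − 4 = 11

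Check: 64 + 45 + 11 = 120.

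**Start time under each reading of first evidence on the tools:**

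| Criteria met | One abnormal sign is enough | Two abnormal signs needed | Full definition, with source, needed on the tool |
|---|---|---|---|
| At least two vital signs (64) | start | start | no start |
| Exactly one (45) | start | none, unless a second sign follows | no start |
| None (11) | none, unless a sign follows | none, unless two signs follow | no start |

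A sign that follows gives a late start, possibly after antibiotics. No column gives every case a start that matches the definition.

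**Sensitivity to the list layout.** In the text as extracted, pCO2 could be an alternative to tachypnoea rather than a separate item. There would then be six criteria and C(6,2) = 15 pairs: 3 with two vital signs, 3 × 3 = 9 mixed, C(3,2) = 3 with none. Sets of two or more: 2^6 − 1 − 6 = 57, of which (3 + 1) × 2^3 = 32 have at least two vital signs, 3 × (2^3 − 1) = 21 exactly one and 2^3 − 1 − 3 = 4 none. This counts the combined item as tool-visible, although it could be met on pCO2 alone. The mismatch remains.

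**Early starts, illustration only.** If a share p of episodes starts h hours early, the arm mean rises by p × h. With assumed p = 0.10 and h = 24 this is 2.4 h; with p = 0.30 and h = 72 it is 21.6 h. A median moves less: if all early-started intervals exceed the rest, p = 0.10 puts it at 0.5/0.9, about the 56th percentile of the correctly started intervals. Neither p nor h is in the documents.

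**The case against.** **Section 4.1.1 can be read in sequence.** It defines sepsis, says which signs matter most for a study of monitoring tools, then times from first evidence of sepsis on those tools. A case definition and a time zero may differ without contradiction. This is fair, but the two must still connect, and for cases with fewer than two vital signs the text gives no connection or an ambiguous one.

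**A reader might infer that laboratory-defined cases never have a start.** The documents do not support that. Absence is clear only where no vital sign qualifies, and even there a later sign may supply a late start. A case with white cell count plus tachycardia has a start if one sign is enough. Altered mental status, one of the four criteria outside the tools, is clinical rather than laboratory.

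**A reader might infer that postoperative tachycardia starts the clock days early.** That is a permitted literal reading, not the stated rule. Sepsis has just been defined as needing an infection source, and on a strict reading tachycardia from pain would not qualify. But on that strict reading the tools alone could never start the clock.

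**Derivation rules are often left to the analysis plan, and no formal comparison is planned.** Look-back windows can indeed go there. The mismatch, however, lies in the primary outcome as the protocol fixes it. The outcome will be summarised by arm, and efficacy is among the objectives in Section 3. Dates not captured on the paper CRFs would need fresh abstraction later.

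**Conclusion.** The point holds as a mismatch in the primary outcome. The start rule does not fit the case definition, and it is open to readings that give different times for the same patient. Of the 120 qualifying sets, 11 have no assigned start or only a late one, and 45 depend on an unstated choice between one sign and two. This rests on the protocol's own description of what each tool records and on reading the list as seven items.

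Three stronger conclusions do not follow.
- The 3 of 21 pairs made up of vital signs alone, like the other counts, describe routes through the definition. They are not shares of patients.
- The hours of shift shown above rest wholly on assumed inputs, and Section 5.1.3 does not name the mean as the summary. The effect on the results cannot be quantified from the documents.
- The one-hour antibiotic target in Section 2.1 is background. No comparison of the outcome with it is planned.

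**What to change.** State one start rule in Section 4.1.1, identical in both arms and matching the case definition:

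- Time zero is when the second listed criterion from any source (tool, clinical or laboratory) was recorded, within a fixed window on both sides of the first documented suspicion of infection, for example 24 h before to 24 h after. The window must extend past suspicion, because blood tests prompted by suspicion report after it.
- Derangements that resolved before the window do not start the clock.
- Episodes whose second criterion is recorded only after antibiotics are counted and reported separately.
- A sensitivity summary is given with another window length.

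Add CRF items for the date and time of each criterion and of the first documented suspicion of infection.

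The cost is protocol wording and a few dated items, taken from admission information that Section 4 already collects after discharge. There are three drawbacks: the window length is a choice, very early warning signs outside it are not counted, and documented suspicion comes from unblinded staff, so patch alerts could bring it forward. The change concerns measurement only and leaves clinical management as it is.

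### The primary interval starts at first evidence on whichever tools a patient has, so time zero depends on the arm and a gain in detection time cannot show as a shorter interval

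*Protocol*

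**What the plan says.** Section 4.1.1 first gives the primary outcome as "Time to treatment of sepsis, specifically time to administration of antibiotics after first evidence of sepsis". It then defines sepsis as a likely source of infection plus two or more listed criteria, and notes that temperature, heart rate and respiratory rate are measured by both systems. Finally it fixes the measure as the "time interval between the first evidence of sepsis on either or both monitoring tools and the administration of antibiotics to the patient".

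The tools differ by arm (section 4, Study design). For the intervention: "Eligible patients in the 'patch' bays/side rooms will receive a patch and standard NEWS monitoring". For control: "Patients in the 'control' bays/side rooms will receive standard NEWS monitoring alone".

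The sampling rates differ widely. For NEWS, section 2.2.1 says: "Vital signs are taken at predetermined intervals (typically 4-hourly), with patient deterioration possible between recordings". The same section describes half-hourly rounds in the first hours after surgery, then 2-hourly, then 4-hourly, and twice-daily recording near discharge. For the patch, section 2.2.3 says: "The data is transmitted wirelessly every two minutes to a central monitoring station".

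The hypothesis in section 2.3 is that the patch added to NEWS "will allow earlier detection of postoperative complications". Section 3 sets an objective that includes efficacy against NEWS alone. Section 5.1.3 summarises each outcome by arm and plans no formal comparison; section 10.1 has no sample size calculation.

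**The concern.** Time zero is the earlier of patch and NEWS evidence in one arm, and NEWS evidence in the other. The delay between deterioration and the next observation round is what the patch is meant to remove. In the control arm that delay falls before the clock starts and is not counted. In the patch arm the clock is already running during it.

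The two by-arm summaries therefore measure different things. If staff act on every alert, the gain in time to antibiotics disappears from the outcome. If they act on only some alerts, the patch arm can show a longer interval although its patients were treated sooner. No secondary outcome in section 4.1.2 measures time to detection, so the loss is not recovered elsewhere. Nor can analysis repair it, because evidence arising between rounds in control patients is never recorded: the protocol describes no concealed patch recording in that arm.

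**Working it through.** The protocol gives no figure for this point, so there is none to reproduce. The check is a short decomposition, and simulation of 1,000,000 episodes per setting at 2-, 4- and 12-hourly rounds agrees with it.

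**From the protocol:** NEWS gap G of 0.5, 2, 4 (typical) or 12 h (section 2.2.1); patch transmission every 2 minutes (sections 2.2.3 and 4).

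**Assumed, not in the protocol:** onset is uniform between rounds; both tools apply the same criteria without error or interruption; the time R from staff acting to antibiotics has the same distribution in both arms (lognormal, median 1.5 h, mean 1.80 h); staff act on patch evidence with probability q and otherwise at the next NEWS round.

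**Step 1, clock start.** Let U be the time from onset to the next NEWS round, uniform on (0, G), and P the time to the next patch transmission, uniform on (0, 2 min). The control clock starts at U and the patch-arm clock at min(U, P). Since min(U, P) ≤ U, the patch-arm clock never starts later for the same onset.

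**Step 2, mean lead time.** L ≈ G/2 − 1 min, that is G/2 − 0.017 h. (Using the minimum rather than P alone changes this by less than 0.001 h.)

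| NEWS gap G | G/2 | Lead time L |
|---|---|---|
| 0.5 h | 0.25 h | about 0.23 h |
| 2 h | 1.00 h | 0.98 h |
| 4 h | 2.00 h | 1.98 h |
| 12 h | 6.00 h | 5.98 h |

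**Step 3, effect on the outcome.** Patch minus control:

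- true difference, onset to antibiotics: −qL
- measured difference under section 4.1.1: (1 − q)L
- so measured difference = true difference + L.

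At G = 4 h the control interval as defined is 1.80 h, and control onset-to-antibiotic time is 2.00 + 1.80 = 3.80 h.

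| Share of alerts acted on, q | Patch interval as defined | Measured difference | Patch onset to antibiotics | True difference |
|---|---|---|---|---|
| 0 | 3.78 h | +1.98 h | 3.80 h | 0.00 h |
| 0.5 | 2.79 h | +0.99 h | 2.80 h | −0.99 h |
| 1 | 1.80 h | 0.00 h | 1.81 h | −1.98 h |

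At q = 0.5 the sign is reversed.

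**Step 4, what can shorten the interval.** A change in R can. If every alert is acted on and the response is 20% faster, the measured difference is −0.20 × 1.80 = −0.36 h.

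**Step 5, clock anchored on NEWS in both arms.** The control mean is still 1.80 h. The patch mean becomes 1.80 − qL, so the difference is −qL, the true one. At G = 4 h and q = 1 the patch mean is 1.80 − 1.98 = −0.18 h, so negative intervals will occur and need a rule. The identity is exact for means; medians need not match it exactly.

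**The case against.** The strongest reply is that this is a feasibility study with no formal comparison, and that HDU/ICU use, length of stay and complications do not depend on this clock. That lowers the consequence. It does not make the two summaries comparable: they will be set side by side under an efficacy objective, and section 1.5 says the results will inform whether the system improves outcomes. The protocol describes no later trial into which an estimate would be carried, so the point does not rest on one.

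The size is also open to challenge. NEWS frequency follows the patient's condition, and at half-hourly rounds the shift is only about 0.23 h. The 12-hourly figure applies mainly near discharge. Patch suspension in critical care (section 4) and patients who stop wearing the patch (counted in section 4.1.2) would dilute the shift under intention-to-treat. All of this stands. It affects the amount, not the direction.

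Two stronger readings are tempting and are not supported:

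- *The patch cannot improve the primary outcome.* It can, because alerts reach a device the nurse carries and may speed the response to evidence already recorded. The equal-response assumption sets that route aside.
- *An isolated heart rate above 90 could start the clock days before sepsis.* Section 4.1.1 places its definition, a likely source plus two or more criteria, directly above the clock rule, and first evidence of sepsis is naturally read in that light. How criteria from different tools and the laboratory combine is not spelled out, but that detail may sit in a statistical analysis plan.

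**Conclusion.** The point holds. Under section 4.1.1 as written, time zero is ascertained differently in the two arms, and the measured difference equals the true onset-to-antibiotic difference plus the lead time. The direction needs only that both tools look for the same evidence and that controls lack one of them. The size, 1.98 h at the typical 4-hourly round and about 0.23 h to 5.98 h across the frequencies the protocol describes, rests on uniform onset, error-free tools and equal response times. For scale, section 2.1 cites a one-hour target for antibiotics.

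It does not follow that the patch will look harmful. With every alert acted on and equal response the measured difference is zero, and with a faster response it favours the patch. What follows is that the primary outcome cannot show the benefit the study hypothesises, and may show its opposite.

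**What to change.** In section 4.1.1:

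- Start the clock in both arms at the first routine NEWS set at which the protocol's own sepsis definition is met (likely source plus two or more criteria).
- Flag alert-triggered NEWS sets on the CRF, so that they do not start the clock.
- Keep patients who receive antibiotics before or without NEWS evidence, as zero or negative intervals or as a separately reported category. Dropping them would remove the patch's successes.
- Summarise with medians or ranks.
- Report the interval as now defined, patch-evidence-to-NEWS time and patch-evidence-to-antibiotic time as patch-arm process measures only, not as a contrast between arms.

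The cost is a change of wording, a CRF flag and time-stamped NEWS and laboratory data; NEWS is already recorded in both arms. Three downsides should be stated. Some intervals will be zero, negative or undefined. NEWS frequency and laboratory testing may still respond to alerts, so the clock becomes much less arm-dependent but not perfectly neutral. The time stamps must be reliable enough to order NEWS, laboratory results and antibiotics.
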